2.2 Study Design and Outcomes (full description in Section 14.0)

Individuals who are active in medication treatment for opioid use disorder (MOUD) with buprenorphine for at least 2 weeks will be invited to participate in the study. This project will evaluate the feasibility and benefits of digital health technologies that can be embedded in clinical trials. Feasibility will be evaluated by the percentage of eligible participants who enroll and adhere to a 12 week period of assessment using passive mobile sensing devices (smartwatch and smartphone), daily randomly prompted EMAs (that assess sleep, stress, pain severity, pain interference, pain catastrophizing, craving, withdrawal, substance use risk context, mood, context, substance use, self-regulation, MOUD adherence, and impact of COVID-19), self-initiated substance use EMA, and social media data download. Participating in the social media data download portion of the study will be optional. The secondary outcomes will be treatment retention and buprenorphine adherence through EMA and EHR/medical claims data over 12 weeks (specifically, the 12 weeks of study participation as well as the 12 months prior to when the individuals start EMAs).

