2.6 Analyses (Full Description in Section 14.0)

[figure not shown]
In order to measure the feasibility of digital health technology, we will generate descriptive statistical summaries of the level of adherence of study participants to the desired protocol (e.g., EMA response rate, smartwatch and smartphone wear/carry rate). No statistical inference is planned for this assessment. Feasibility will be evaluated via the following three independent metrics: 1) the percentage of days during the 12-week active phase enrolled participants wore/carried the smartwatch and smartphone; 2) the response rate to EMA prompts during the 12-week active phase; and 3) the percentage of participants who consent to social media data download and sparsity of social media data per participant.

In digital health data (Jain, Powers, Hawkins, & Brownstein, 2015a), the spatio-temporal granularity of information about an individual is of higher resolution than that obtained through cross-sectional or traditional longitudinal studies. Therefore, we define endpoints (dependent variables) that may occur repeatedly over a 12-week observational period, and aim to use data from smartphones, wearable devices, social media and EMA to predict, explain and detect these endpoints.

Our analyses comprise three main efforts: Predicting endpoints using passively and actively collected digital health and social media data; Explaining temporal-causal relationships between factors determined to be useful for predicting endpoints; Detecting event-specific endpoints using passively collected digital health and social media data.

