6.2 Duration of Study and Visit Schedule

Participants will complete screening by phone/video (approximately 10 minutes) and two to three baseline phone/video appointments which will take approximately 2.0 hours. The study involves a 12-week active phase wherein participants will wear a smartwatch, carry a smartphone, and respond to EMA prompts and self-initiated EMAs through a smartphone. For those who consent, social media data will be downloaded by the participant directly from the social media platform to a secure server using a remote desktop at the beginning of the study and again at the end of the study. A follow-up phone/video appointment (approximately 60 minutes) will occur approximately 12 weeks post-EMA start. EHR and medical claims data will be extracted by the research staff approximately 16-weeks after study completion and includes data 12 months prior to EMA start through 12 weeks post-EMA start.

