7.2 Secondary Outcome Measure(s)

The secondary outcome measures will include:

1. OUD treatment retention (days retained in OUD treatment program) based on EHR data;
2. Days covered on MOUD based on EHR and EMA data; and
3. Non-prescribed opioid use (including illicit opioid use) based on EMA data.

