14.1.2 Primary and Secondary Outcomes (Endpoints)

The primary outcomes will include: (1) the percentage of days during the 12-week active phase enrolled participants wore/carried the smartwatch and smartphone; (2) response rate to EMA prompts during the 12-week phase; and (3) the percentage of participants who consent to social media data download and sparsity of social media data per participant.

The secondary outcome measures will be: (1) OUD treatment retention (days retained in OUD treatment program) based on EHR data; (2) Days covered on MOUD based on EHR and EMA data; and (3) Non-prescribed opioid use based on EHR and EMA data.

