14.3 Statistical Methods for Primary and Secondary Outcomes

For our primary and secondary outcomes, we intend to use measures such as precision, recall (sensitivity) and specificity, F-score, to assess the quality of our predictions. The quality of the

identified digital phenotypes will be evaluated using cohesion (e.g., Silhouette score) and endpoint-differentiating power (e.g., Z-score).

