14.5 Types of Analyses

We are interested in measuring and predicting outcomes that may occur repeatedly over a 12-week observational period (e.g., patterns of daily drug use) using digital health technology. In digital health (Jain et al., 2015a) the spatio-temporal granularity of information about an individual is of higher resolution than that obtained through cross-sectional or traditional longitudinal studies. We will therefore assess the utility of using data from smartphones, smartwatches, social media and ecological momentary assessment to predict, explain and detect these outcomes.

Predicting outcomes using passively and actively collected digital health and social media data: Our approach to prediction will include regression-based methods (e.g., logistic regression), but we will also use common machine learning approaches for binary classification (e.g., random forest, support vector machines, K-means, gradient boosting). For each of these classification techniques, we will assess the utility of the various digital data for improving prediction quality. Typical evaluation methods used to assess the prediction quality include accuracy, precision, F-score, sensitivity (recall), and specificity. The relative utility of the various data for predicting outcomes will be assessed at two levels - individual features level and aggregated feature level. Interpretability of each feature and its contribution in predicting the outcome variable will be assessed using an ensemble framework, SHAP (Lundberg & Lee, 2017). In addition, we will also assess mutual information (Kraskov, Stogbauer, & Grassberger, 2004), which is a non-parametric approach of estimating the dependency between individual features and the target outcome. In another approach, features will be aggregated based on their gross categories (e.g., Facebook, Twitter, GPS, step, sleep, mood). The relative importance of each category will be evaluated based on its performance in predicting outcome (e.g., F-score).

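### Days retained and days covered are day counts, but the prediction measures named in 14.3 and 14.5 are all classification measures, and section 14 does not say how either outcome becomes a class

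*Combined protocol and SAP*

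**What the plan says.** **Outcomes.** Sections 7.2 and 14.1.2 give the first secondary outcome as "OUD treatment retention (days retained in OUD treatment program) based on EHR data" and the second as "Days covered on MOUD based on EHR and EMA data". Section 2.2 sets their window as "the 12 weeks of study participation as well as the 12 months prior to when the individuals start EMAs". Section 6.2 places the digital collection later: "The study involves a 12-week active phase wherein participants will wear a smartwatch, carry a smartphone, and respond to EMA prompts".

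**Measures and models.** Section 14.3 covers the "primary and secondary outcomes, we intend to use measures such as precision, recall (sensitivity) and specificity, F-score, to assess the quality of our predictions". Section 14.5 adds accuracy to these measures. As models it names regression-based methods, with logistic regression as the example, and machine learning for binary classification, with four examples. One of these is K-means, where the parallel list in 2.6 has K-nearest neighbor.

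**Comparing sources.** The secondary objective (5.2) sets EMA, sensing and social media data against one another. For groups of features, 14.5 says: "The relative importance of each category will be evaluated based on its performance in predicting outcome (e.g., F-score", so F-score is an example there. Individual features are also assessed by SHAP and by mutual information, described as a "non-parametric approach of estimating the dependency between individual features and the target outcome".

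**Nearby text.** Section 2.6 says "we define endpoints (dependent variables) that may occur repeatedly over a 12-week observational period". Section 7.3 item 2, listed among the other outcomes, is a yes/no variable: share of days with medication access above a threshold, for example 80%, over 12 weeks, from EHR data. Items 4 to 6 are single events: non-prescribed opioid use, missed dose, missed visit. Section 14.7 refers to an Extended Data Analytic Plan.

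**The concern.** Precision, recall, specificity and F-score need a yes/no label. A day count has none until someone chooses a cut-off, decides whether the unit is the person or the day, and names the class counted as positive. Section 14 makes none of these choices for the two day counts, and it names no measure, such as a prediction error, that would suit a count or a duration.

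This matters for the secondary objective. F-score depends on all three choices, and a rule that ignores the data can score highly on it. If the choices are made after the data are seen, the ranking of the sources could depend on them, and a high F-score need not show that the digital data helped.

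A related difficulty is that days covered draws on EMA data while EMA is one of the sources being compared. If EMA adherence reports sit in the outcome and among the predictors, EMA has a built-in advantage.

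**Working it through.** The plan gives no figure on this point, so there is nothing to reproduce. The check sets the text side by side and then illustrates the size.

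**Step 1. Outcome against tool.**

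| Outcome | Scale | Class defined? | Do the named measures fit? |
|---|---|---|---|
| Days retained (7.2, 14.1.2) | Count | No | Not as defined |
| Days covered (7.2, 14.1.2) | Count | Example 80% in 7.3 item 2; EHR only; not linked in section 14 | Only if linked and fixed |
| 7.3 items 4 to 6 | Events | Yes, by nature | Yes |
| Primary feasibility outcomes | Percentages, rates, sparsity | Not applicable | No; 14.5 item 3 plans descriptive summaries |

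The 7.3 item 2 threshold works out as 12 × 7 = 84 days and 0.80 × 84 = 67.2, so exceeding it means at least 68 days.

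**Step 2. Window.** EMA and sensor data exist only in the 12-week active phase. The 12 months before EMA start, which 2.2 adds, therefore cannot be predicted by all three sources; the 12 weeks can.

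**Step 3. The no-data rule.** F = 2TP/(2TP + FP + FN). Let p be the share retained (assumed; the documents give none) and call everyone retained. With retained as the positive class, F = 2p/(1 + p). With not retained as positive, and everyone called not retained, F = 2(1 − p)/(2 − p). A source that is right for the same share x of both groups has F = 2px/(2px + 1 − x), which exceeds 2p/(1 + p) only when x > 1/(2 − p).

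| p | F, retained positive | F, not retained positive | x needed |
|---|---|---|---|
| 0.6 | 0.750 | 0.571 | 0.714 |
| 0.7 | 0.824 | 0.462 | 0.769 |
| 0.8 | 0.889 | 0.333 | 0.833 |
| 0.9 | 0.947 | 0.182 | 0.909 |

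**Step 4. Two sources.** Assume 50 people, 40 retained. Source A is right for 36/40 retained and 5/10 not retained; source B for 32/40 and 8/10.

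- Retained positive: A = 72/(72 + 5 + 4) = 0.889; B = 64/(64 + 2 + 8) = 0.865; no-data rule = 80/(80 + 10) = 0.889. Specificity is 0.5, 0.8 and 0 respectively.
- Not retained positive: A = 10/(10 + 4 + 5) = 0.526; B = 16/(16 + 8 + 2) = 0.615.

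The order reverses. Under the first choice A only equals the no-data rule and B falls below it.

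**Step 5. How often.** Let the share right in each group run from 0.50 to 0.95 in steps of 0.05. That gives 10 × 10 = 100 sources and 100 × 99/2 = 4,950 pairs. Changing the positive class reverses the F-score order in:

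| p | Pairs reversed | Of these, F gap below 0.05 under at least one class |
|---|---|---|
| 0.6 | 852 (17.2%) | 699 (82%) |
| 0.7 | 764 (15.4%) | 644 (84%) |
| 0.8 | 653 (13.2%) | 570 (87%) |
| 0.9 | 520 (10.5%) | 475 (91%) |

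Most pairs do not reverse, and most reversals involve a near-tie. The grid is an illustration, not a forecast. It varies the positive class only, not the cut-off.

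**Step 6. Unit.** One label per person gives 50 labels (up to 75). One per day gives up to 50 × 84 = 4,200 (75 × 84 = 6,300) correlated labels.

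**The case against.** The strongest reply is that the lists are open and the tools suit much of what is planned. This largely stands.

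- Regression-based methods are a general class with logistic regression as one example, and the measures are introduced as examples or as typical. A reader might infer that the plan permits only binary classifiers. It does not say so. K-means takes no label at all, and mutual information is not limited to classes.
- A reader might infer that no cut-off exists for coverage. In substance 7.3 item 2 is a person-level yes/no form of it over 12 weeks. What is missing is a fixed value and a link from section 14. Its source also differs: EHR alone, against EHR and EMA for days covered. Days retained has no such counterpart.
- The repeated endpoints of 2.6, and the detection of drug-use and non-adherence events in 14.5 item 2, fit the named measures. They do not settle how a total of days per person is handled.
- Specificity is listed beside F-score and would expose the no-data rule, whose specificity is 0.
- The Extended Data Analytic Plan may define the labels. It is cited only under exploratory analysis and cannot be checked here, so absence from the whole plan is not shown.

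What remains is that section 14, which sets the methods for these outcomes, neither names a measure for a day count nor says how the counts become classes.

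**Conclusion.** The point holds in this limited form. Both outcomes are defined as day counts, the named measures are all for classes, and section 14 supplies no bridge between them. The conversion of days retained is undefined. For days covered, use of the 80% example is left open. No positive class is stated for either.

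The consequence is confined to the secondary comparison of data sources, in a study that its synopsis describes as a pilot not powered to test specific hypotheses. The primary feasibility objective is unaffected. Section 14.3 might be read as planning to score the primary outcomes by F-score, but 14.5 item 3 gives them descriptive summaries, so the wording of 14.3 needs tidying and nothing more follows. Nor do the figures show that the ranking of sources will reverse. They show that it can, under assumed retained shares and accuracies, and that in most pairs it does not.

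The change is worth making because it is cheap and makes the secondary comparison interpretable.

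**What to change.** 1. In 14.3, limit the prediction measures to the secondary and other outcomes, and refer the primary outcomes to the descriptive summaries in 14.5 item 3.
2. Predict days retained and days covered on their own scale over the 12-week window, with a matching out-of-sample measure. Examples are time to leaving treatment with a C-index, or proportion of days with a prediction error. If binary labels are kept, fix cut-off, unit and positive class before the data are seen; for days covered this can be done by linking 7.3 item 2 and fixing its threshold. If the Extended Data Analytic Plan already does this, a cross-reference in 14.3 is enough. Say what role the prior 12 months in 2.2 play.
3. Compare data sources on an EHR-based days-covered outcome and report the EMA-based version separately, so that EMA is not both predictor and outcome.
4. Report every source against a no-data benchmark, with specificity beside F-score.
5. Reconcile K-means in 14.5 with K-nearest neighbor in 2.6.

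The cost is SAP wording and a little more analysis work. No new data are needed.

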14.4 Significance Testing

The primary outcome will be evaluated using a two-sided test with a type I error rate of 5%. There are several secondary outcomes; however, multiple comparisons will not be adjusted for since these are not part of the study's primary objective as an observational study.

14.5 Types of Analyses

We are interested in measuring and predicting outcomes that may occur repeatedly over a 12-week observational period (e.g., patterns of daily drug use) using digital health technology. In digital health (Jain et al., 2015a) the spatio-temporal granularity of information about an individual is of higher resolution than that obtained through cross-sectional or traditional longitudinal studies. We will therefore assess the utility of using data from smartphones, smartwatches, social media and ecological momentary assessment to predict, explain and detect these outcomes.

Predicting outcomes using passively and actively collected digital health and social media data: Our approach to prediction will include regression-based methods (e.g., logistic regression), but we will also use common machine learning approaches for binary classification (e.g., random forest, support vector machines, K-means, gradient boosting). For each of these classification techniques, we will assess the utility of the various digital data for improving prediction quality. Typical evaluation methods used to assess the prediction quality include accuracy, precision, F-score, sensitivity (recall), and specificity. The relative utility of the various data for predicting outcomes will be assessed at two levels - individual features level and aggregated feature level. Interpretability of each feature and its contribution in predicting the outcome variable will be assessed using an ensemble framework, SHAP (Lundberg & Lee, 2017). In addition, we will also assess mutual information (Kraskov, Stogbauer, & Grassberger, 2004), which is a non-parametric approach of estimating the dependency between individual features and the target outcome. In another approach, features will be aggregated based on their gross categories (e.g., Facebook, Twitter, GPS, step, sleep, mood). The relative importance of each category will be evaluated based on its performance in predicting outcome (e.g., F-score).

1. *Explaining temporal-causal relationships between factors determined to be useful for predicting outcomes:* Although machine learning methods may often be more effective for prediction than simple regression or correlation, they may be difficult to explain, or may not reveal insights regarding the relationships between factors. Therefore, we also include a set of analyses that are conducive to generating such explanatory or descriptive insights. For example, we will apply supervised metric learning and prototypical case-based reasoning (Hsueh et al., 2018), topic-modeling (e.g., Latent Dirichlet Allocation) and causal inference methods (Cheng, Bahadori, & Liu, 2014; Kleinberg & Hripcsak, 2011).
2. *Outcome detection using passively collected digital health data:* We plan to measure drug use and medication non-adherence events via EMA, multiple times a day. Since EMA requires a level of active engagement from participants that may not be realistic to expect outside of a research study, we plan to use machine learning to detect these events using only passively collected data. The methods used here would be similar to the machine learning methods previously described for binary classification.
3. *Feasibility of digital health technology:* We will generate descriptive statistical summaries of the level of adherence of study participants to the desired protocol (e.g., EMA response rate, smartwatch and smartphone wear/carry rate). No statistical inference is planned for this assessment.

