Advances in **digital technologies and data analytics** have created new opportunities to assess and modify health behavior and thus accelerate the ability of science to understand and contribute to improved health behavior and health outcomes. Given the ubiquity of access to digital technology worldwide, digital technologies afford new opportunities to examine within-person differences in health behavior through intensive collection of individual-level data using mobile devices, wearable sensors, continuous monitoring, and mapping digital footprints. Digital technologies can also enable widespread reach and scalability of evidence-based, anytime/anywhere access to personalized interventions (Marsch, Lord, & Dallery, 2014). Specifically, mobile technologies enable EMA, (Shiffman, Stone, & Hufford, 2008) a method that prompts individuals to respond to queries (e.g., regarding positive and negative affect, context, access to opioids, urge to use (craving), drug use, withdrawal, perceived stress, sleep/sleep disturbance, and perceived pain) on mobile devices, and which enables “automated hovering” (Asch, Muller, & Volpp, 2012) or real-time monitoring, of individuals’ behavior while they engage in everyday activities and over time. The frequent, longitudinal assessment afforded by EMA in naturalistic contexts may clarify the dynamic role of mechanisms, or reveal new mechanisms, contributing to health behavior (McCarthy et al., 2008) in individuals who use opioids or who are in treatment for opioid use.

Digital technologies also enable **passive sensing and inference** from smartphones or sensing devices worn on the body, which is transforming how we understand human behavior, including health behavior. These mobile sensing technologies enable the continuous measurement of physiological and behavioral data in the real world as individuals move through their daily lives. This sensor data can be wirelessly streamed to a smartphone and processed in real-time on the mobile device to infer information about an individual’s behavior, health, and environment. These data from sensors can be combined with data from self-report EMA assessments embedded on mobile devices for real-time inference of environmental, social, and behavioral conditions (Marsch, 2018a, 2018b). In the future, this information could be used to prompt the delivery of interventions in real time (e.g., interventions that are directly responsive to the behavioral health

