7.3 Other Outcome Measures

Other outcomes will include:

1. Frequency of missed buprenorphine doses based on EMA data;
2. Percentage of days with access to prescription medication exceeding a threshold (e.g., 80%) over the 12-week study period (a dichotomous variable based on pharmacy dispensation and medication orders from the EHR data extraction);
3. Number of days of non-prescribed opioid use (including illicit opioid use) in the last 4 weeks (weeks 9-12 post study consent) based on EMA data; and
4. Each non-prescribed opioid use event during the 12-week study period based on EMA data.
5. Each missed dose event during the 12-week study period based on EMA data.
6. Each missed visit to OUD treatment program during the 12-week study period based on EHR data.

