11.5.2 Ecological Momentary Assessment (EMA)

Participants will be prompted up to 3 times per day over 12 weeks by the smartphone app to self-report sleep, stress, pain severity, pain interference, pain catastrophizing, craving, withdrawal, substance use risk context, mood, context, substance use, self-regulation, MOUD adherence, and the impact of COVID-19 (Buysse, Reynolds, Monk, Berman, & Kupfer, 1989; Freeman & Gottfredson, 2018; Kuerbis et al., 2019; Preston et al., 2017, 2018). The EMA prompt delivery times will be randomized within each of the prompt timeframes (e.g., morning, mid-day, end of day). In addition to prompted EMAs, participants will be asked to self-initiate EMAs if substance use occurred (e.g., opioids, cocaine, or other stimulants). All EMA data collected via the smartphone will be securely transmitted to a secure cloud-based database housed in the Research Computing Department at Dartmouth College.

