14.2.2 Projected Number of Participants per Site

Approximately 50 (if recruitment is faster than anticipated, we will recruit up to 75) participants are projected to be recruited from KPNC.

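### Sections 14.3 and 14.5 name logistic regression for event and person-day outcomes without allowing for up to 84 correlated days per participant

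*Combined protocol and SAP*

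**What the plan says.** Section 14.5 opens with the repeated nature of the outcomes: "We are interested in measuring and predicting outcomes that may occur repeatedly over a 12-week observational period (e.g., patterns of daily drug use". It continues: "Our approach to prediction will include regression-based methods (e.g., logistic regression", followed by several machine-learning classifiers. Prediction quality is judged by classification metrics, and the contribution of features by SHAP and mutual information.

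The repetition is explicit elsewhere. Item 4 of Section 7.3 reads "Each non-prescribed opioid use event during the 12-week study period based on EMA data"; items 5 and 6 treat missed doses and missed treatment visits in the same way. Section 11.5.2 gives the sampling density: "Participants will be prompted up to 3 times per day over 12 weeks by the smartphone app". Section 14.2.2 gives the number of people: "Approximately 50 (if recruitment is faster than anticipated, we will recruit up to 75) participants are projected to be recruited from KPNC".

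Section 14.3 adds that digital phenotypes will be "evaluated using cohesion (e.g., Silhouette score) and endpoint-differentiating power (e.g., Z-score". Section 14.4 says: "There are several secondary outcomes; however, multiple comparisons will not be adjusted for".

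None of the supplied text mentions a participant random effect, GEE, a clustered variance, or resampling by participant.

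**The concern.** The independent units are 50 to 75 people, whereas the analysis file for event and person-day outcomes could hold thousands of rows. A logistic regression fitted to those rows with its usual model-based variance counts each row as new information. Repeated days from one person partly repeat that person's own level of risk.

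The consequence is selective. A feature that mainly marks who someone is (for example a habitual activity level, or a summary of social media data downloaded only at the start and end of the study) is in effect observed once per person but credited with up to 84 observations. It can then appear to predict daily opioid use or missed doses when it does not. Section 2.4 says the results are meant to inform other studies and trials in this population, so such features could be carried forward.

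**Working it through.** **Inputs**
- Days per person: 12 weeks × 7 = 84 at most; prompts: 84 × 3 = 252 at most (Section 11.5.2).
- Participants: 50 to 75 (Section 14.2.2), so 50 × 84 = 4,200 to 75 × 84 = 6,300 person-days.
- ICC of the daily outcome: not in the documents. Assumed values 0.01, 0.05 and 0.10.
- The plan gives no standard error, interval or power for these analyses, so there is no figure of its own to reproduce.

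**Person-constant feature**

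Design effect (DEFF) = 1 + (m − 1) × ICC. The true standard error (SE) is √DEFF times the naive one. A nominal two-sided 5% test then rejects a true null with probability 2 × [1 − Φ(1.96/√DEFF)]. With m = 84:

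| ICC | DEFF | SE ratio | Actual type I error | 4,200 days worth |
|---|---|---|---|---|
| 0.01 | 1 + 83 × 0.01 = 1.83 | 1.35 | 15% | 2,295 |
| 0.05 | 1 + 83 × 0.05 = 5.15 | 2.27 | 39% | 816 |
| 0.10 | 1 + 83 × 0.10 = 9.30 | 3.05 | 52% | 452 |

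If only half the days are observed (m = 42), the ratios fall to 1.19, 1.75 and 2.26. They do not depend on whether 50 or 75 people enrol.

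**Feature with only part of its variance between people**

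DEFF ≈ 1 + (m − 1) × ICC(outcome) × ICC(feature). With half the feature's variance between people and m = 84:
- ICC 0.01: 1 + 83 × 0.01 × 0.5 = 1.415, ratio 1.19.
- ICC 0.05: 1 + 83 × 0.05 × 0.5 = 3.075, ratio 1.75.
- ICC 0.10: 1 + 83 × 0.10 × 0.5 = 5.15, ratio 2.27.

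With no between-person variance in the feature, DEFF = 1 and nothing is understated.

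**Simulation check**

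Null logistic regression, 50 people × 84 days, intercept −2.5, 400 runs per setting. The person intercept has SD 0.5, 1.0 or 1.5 on the logit scale. The latent ICC is SD²/(SD² + π²/3) = 0.07, 0.23 or 0.41. Latent ICCs are not on the same scale as those in the table above.

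| Feature | Clustered SE ÷ naive SE | Naive type I error |
|---|---|---|
| Constant within person | 1.54, 2.70, 3.95 | 25%, 52%, 65% |
| Half person, half day | 1.29, 2.02, 2.91 | 14%, 38%, 51% |
| Independent by day | 0.99, 0.99, 0.97 | 5.5%, 5.5%, 4% |

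The ratios for the person-constant feature correspond to observed-scale ICCs of (ratio² − 1)/83, about 0.02, 0.08 and 0.18. For the day-varying feature the departures from 5% are within simulation error: √(0.05 × 0.95/400) is about 1.1 percentage points.

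Uncorrected cluster-robust tests rejected in about 6% to 9% of runs across all nine settings. They remove most of the inflation, but with 50 clusters not reliably all of it.

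**The case against.** The strongest reply is that there is nothing yet to be too narrow. Sections 14.3 and 14.5 list point measures for prediction and specify no intervals or p-values. The 5% test in Section 14.4 is attached to the primary outcome, and the Parent Study text in Section 2.0 calls this a pilot without power for specific hypotheses. Logistic regression is only an example, and silence on variance is not a commitment to independent rows. This stands to the extent that the point must be conditional. It does not remove it: the remark in Section 14.4 on unadjusted secondary comparisons presupposes some testing, and Section 14.1.1 states a hypothesis about predicting retention and adherence.

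A reader might infer several stronger things that the documents do not support:
- That the plan's error bars are already far too narrow. None is specified, and the effect ranges from none to large depending on the feature.
- That the Z-scores will be inflated. Section 14.3 ties them to digital phenotypes and does not say whether the unit is a person or a row. Mutual information likewise has no stated interval.
- That the study's stated aim is within-person change. The phrase "examine within-person differences in health behavior through intensive collection of individual-level data" is background in Section 4.1.1 on what the technology permits. The secondary objective in Sections 2.1 and 5.2 is prediction of retention and medication adherence.
- That every outcome is affected. Days retained (Section 7.2, item 1) and the dichotomy at a threshold such as 80% (Section 7.3, item 2) give one value per person.

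Finally, Section 14.7 refers to an Extended Data Analytic Plan that is not among the supplied documents. It may deal with clustering, but this cannot be checked. It is cited only under exploratory analysis, whereas Sections 14.3 and 14.5 carry the methods for the secondary outcomes.

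**Conclusion.** The point holds in a conditional and bounded form. For event and person-day outcomes, the supplied plan names a regression method and makes no provision for repeated records from 50 to 75 people. If rows are treated as independent, standard errors for a person-constant feature over 84 days are understated about 1.35-fold at ICC 0.01, 2.3-fold at 0.05 and 3.05-fold at 0.10. The understatement is smaller for partly stable features and essentially absent for those that vary independently by day.

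This rests on assumed ICCs, on complete data for 84 days, and on intervals or tests actually being computed from rows. The descriptive feasibility summaries and the outcomes with one value per person are not affected. It is worth correcting because the remedy is cheap and the features most at risk are those likely to be mistaken for general predictors.

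**What to change.** In Sections 14.3 and 14.5, state that for person-day and event outcomes:

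1. Regression uses a participant random intercept, or GEE with robust standard errors corrected for a small number of clusters.
2. Any interval, test or Z-score computed from repeated rows is obtained by resampling or permuting whole participants, not rows.
3. Splitting a feature into the person's mean and the daily deviation from it is limited to explanatory models. In a predictive model, a mean taken over all 12 weeks would use data from after the time of prediction.

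If the Extended Data Analytic Plan already says this, a cross-reference from both sections is enough.

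No new data or participants are needed. The costs are some SAP wording, slightly more computing, wider intervals and fewer features called significant.
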